3. BACKGROUND

Acute Myeloid Leukemia (AML)

Acute myeloid leukemia (AML) is a malignancy of immature granulocytes or monocytes. Malignancy is characterized by accumulation of leukemic blasts and blockade of normal bone marrow production resulting in thrombocytopenia, anemia, and neutropenia. In hematologic malignancies, high levels of FLT3 expression have been detected in AML blasts (70%-100%). 1,2

Targeted Therapy in AML

During the past 30 years there has been a steady improvement in the survival of patients diagnosed with AML. New drugs like arsenic trioxide and all-trans retinoic acid (ATRA) have been approved for acute promyelocytic leukemia and immunoconjugates like gemtuzumab ozogamicin were for a period approved for elderly AML patients. However, no new drugs have been approved for the treatment of FLT3 mutant AML.

Biological Role of FLT3

FMS-like tyrosine kinase 3 (FLT3) is a receptor tyrosine kinase with important roles in hematopoietic stem/progenitor cell survival and proliferation. FLT3 belongs to the class III receptor tyrosine kinase (RTK) family, including FMS, c-KIT, platelet derived growth factor receptorα, and platelet-derived growth factor receptorβ. ² The human FLT3 gene is located on chromosome 13q12 and encompasses 24 exons. It encodes a membrane-bound glycosylated protein of 993 amino acids with a molecular weight of 158-160 kDa, as well as a non-glycosylated isoform of 130-143 kDa that is not associated with the plasma membrane.^{3,4} The schematic of FLT3 is provided in Figure 3.1.⁵

[figure not shown]

Figure 3.1. Schematic of FLT3 representing the domains: transmembrane, juxtamembrane and tyrosine kinase and the mutation locations of ITD and KD.⁶

In normal human hematopoiesis, FLT3 expression is restricted to immature hematopoietic progenitors including CD34⁺ hematopoietic stem cells (HSCs). ⁷ FLT3-ligand (FL) stimulation

11

Protocol: ARO-005 Confidential Version – 3.0 (October 27, 2014)

of hematopoietic progenitors without other growth factors prompts monocytic differentiation, whereas combinations of stem cell factor, interleukin (IL)-3, and FL induce proliferation and maintenance of human CD34⁺/CD38⁺ progenitor cells.^{8,9}

Downstream Pathways of Normal FLT3

Binding of the FLT3 ligand is followed by receptor autophosphorylation at tyrosine residues, thereby creating docking sites for signal transducing effector molecules and activating various signaling pathways. The downstream signaling cascade involves the tyrosine phosphorylation and activation of multiple cytoplasmic molecules. The FLT3 cytoplasmic domain physically associates with the p85 subunit of phosphoinositol-3-kinase (PI3K), Ras GTPase, phospholipase C-g, Shc, growth factor receptor bound protein (Grb2) and Src family tyrosine kinase, and results in the phosphorylation of these proteins. These actions affect the activation of further downstream PI3K/protein kinase B (Akt) and mitogen-activated protein kinase (MAPK) pathways. Bruserud et al. reported that exogenous FL increases blast proliferation for not only patients with wild-type FLT3 but also patients with FLT3-ITD, as well as, FLT3-TKD mutations. Therefore, FL-mediated triggering of FLT3 appears to be important for both wild-type and mutant FLT3 signaling.

FLT3 Mutations in AML

Protocol: ARO-005

In hematologic malignancies, high levels of FLT3 expression have been detected in AML blasts (70%-100%). ^{14,15} Mutations within the FLT3 gene have been detected in up to 35% of acute myeloid leukemia (AML) patients and represents one of the most frequently identified genetic alterations in AML. ¹⁶ Two major classes of activating FLT3 mutations have been identified in AML patients: internal-tandem duplications (ITDs) and tyrosine kinase domain (TKD) point mutations (Figure 3.1). ⁵ ITDs in the juxtamembrane (JM) domain of FLT3 were first described by Nakao et al and are detected in 20%-25% of AML patients. ITDs are in-frame duplications of 3-400 base pairs. ¹⁷ Recently, FLT3-ITD insertion sites were systematically reviewed in 753 unselected patients with AML positive for FLT3-ITD, and it was demonstrated that 28.7% of ITDs integrate in the TKD1 and not as previously assumed in the JM domain of FLT3. ¹⁸ ITD mutations cause constitutive activation of FLT3, leading to aberrant activation of multiple downstream pathways such as phosphatidylinositol 3-kinase (PI3K)/AKT, mitogen-activated protein kinase/ extracellular signal-regulated kinase (MAPK/ERK), and signal transducer and activator of transcription 5 (STAT5). ¹⁸ FLT3-ITD expression confers factor independent growth in murine IL-3— dependent cell lines and causes a fatal myeloproliferative disorder in murine bone marrow (BM) transplantation models and in FLT3-ITD knock-in mice.

A number of FLT3 inhibitors with *in vitro* and *in vivo* activity against the FLT3 ITD mutation are in clinical development. However, most AML patients who initially respond to these FLT3 TKIs experience relapse. This resistance is mediated through the development of the D835 FLT3 TKD secondary mutation in approximately 5-10% of relapsed AML patients. No FLT3 inhibitor currently in development has the ability to inhibit the FLT3 TKD mutation D835 to treat patients with relapsed AML

4. CRENOLANIB BESYLATE (CP-868,596-26), PRECLINICAL DATA

Crenolanib is a Potent Inhibitor of Type III Receptor Kinases

Crenolanib besylate (CP-868,596-26) is an orally bioavailable selective and potent inhibitor of FLT3, both wild type and FLT3 constitutively active mutations. The chemical name of crenolanib besylate is 4-piperidinamine, 1-[2-[5-[(3-Methyl-3-oxetanyl) methoxy]-1H-benzimidazol-1-yl]- 8-quinolinyl]-, monobenzenesulfonate. ²⁶ The CAS registry number is 670220-93-6.²⁷

Crenolanib is a specific and potent inhibitor of class III receptor tyrosine kinases (RTKs) (Table 4.1). Crenolanib has sub-nanomolar K_d against wild-type FLT3 (0.74nM) and is potent against PDGFR α (3.2 nM) and PDGFR β (2.1nM) (Table 4.1.). Besides class III RTKs, crenolanib does not inhibit any other know RTK (VEGFR, FGFR) or any other serine/threonine kinase (Abl, Raf) at clinically achievable concentrations.

RTK	Crenolanib K _d
FLT3	0.74 nM
PDGFRβ	2.1 nM
PDGFRα	3.2 nM
CFS1R	30 nM
Kit	78 nM

Table 4.1. Activity of crenolanib against type-III receptor kinases²⁶

Crenolanib has high affinity for constitutively active FLT3 mutants,

Crenolanib was evaluated in a K_dELECT assay (DiscoverRx, San Diego, CA) to determine its affinity against FLT3 and its mutant isoforms. The results demonstrate that crenolanib has activity against the FLT3-ITD, the most frequent FLT3 aberration in AML, and the FLT3-TKD D835H and D835Y mutations (Table 4.2).

KINOMEscan Gene Symbol	Publications that first report gene aberration in AML	Crenolanib K _d (nM)
FLT3		0.74
FLT3(ITD)	Leukemia. 10, 1911-1918 (1996).	0.43
FLT3(D835H)	Blood. 97, 2434-2439 (2001); Br J	0.4
FL13(D833H)	Haematol. 113, 983-988 (2001).	0.4
FLT3(D835Y)	Blood. 97, 2434-2439 (2001); Br J	0.18
TL13(D6551)	Haematol. 113, 983-988 (2001).	0.10
FLT3(K663Q)	Leukemia. 20, 2008-2014 (2006).	1.4
FLT3(R834Q)	Cancer Cell. 12, 501–513 (2007).	0.8

Table 4.2. K_d measurements for the interactions of crenolanib with wild type FLT3 and its mutants: FLT3-ITD, FLT3-TKD D835Y, and FLT3-TKD D835H.²⁶

We compared the K_d of crenolanib for wild type and mutant FLT3 with the K_d's of 72 other TKIs. ¹⁹ Crenolanib binds to FLT3-ITD with a K_d of 0.43, as compared to a K_d of 8.8 nM for quizartinib and K_d of 13 nM for sorafenib. Crenolanib binds to FLT3-TKD D835H with a K_d of 0.4 nM, as compared to a K_d of 3.7nM for quizartinib and K_d of 30nM for sorafenib. Similarly, crenolanib also binds to FLT3-TKD D835Y, a mutation that has been shown to cause resistance to quizartinib, with a K_d of 0.18nM, as compared to a K_d of 7.1nM for quizartinib and K_d of 82nM for sorafenib (Figure 4.1). ¹⁹ In addition to the kinome scan, crenolanib inhibition of the FLT3 wild type and FLT3-TKD D835Y mutation was confirmed by Millipore IC50 profiler assay, a system that directly measures phosphorylation with superior sensitivity using phosphocellulose (PH) filter plates. Crenolanib showed potency at 2nM against the FLT3 D835Y mutation and 3 nm against wild type FLT3.

[figure not shown]

Figure 4.1. K_d measurements for the interactions of crenolanib, sunitinib, CEP-701, AC-220 (quizartinib), sorafenib etc, with wild type FLT3 and its mutants: FLT3-ITD, FLT3/D835Y, and FLT3/D835H. Assay signals were normalized to facilitate comparison.²⁸

Immunoblot experiments confirm the activity of crenolanib against FLT3 and its mutants in different cells

In immunoblots, crenolanib inhibited phosphorylation of the wild type FLT3 receptor (in SEMK2 cells), the FLT3-ITD receptor (in Molm 14 and MV411 cells) and the FLT3-D835Y TKD mutation (in transfecting Ba/F3 cells), (Figure 4.2).

[figure not shown]

Figure 4.2 Dose response of crenolanib in various models of FLT3 AML cells: (A) SEMK2 cells, (B) Molm14 cells, (C) MV411 cells, and (D) FLT3-D835Y Ba/F3 cells.²⁷

In SEMK2 cells that express wild type FLT3, crenolanib was effective with a p-FLT3 IC_{50} of 2.11nM.The IC_{50} values of crenolanib against the TF/ITD Molm14 and MV411 cell lines, derived by transfecting TF-1 cells, were 2.65nM and 1.28 nM, respectively. The IC_{50} of crenolanib against the D835Y, TKD mutation of FLT3 was 8.8nM.

Crenolanib is cytotoxic to myeloid leukemia cell lines with FLT3 mutation with concomitant inhibition of FLT3 phosphorylation and its downstream signaling pathways

Crenolanib has been shown to inhibit FLT3 phosphorylation and downstream signaling in both myeloid leukemia cell lines with FLT3-ITD as well as in primary leukemic blasts with FLT3 ITD or TKD mutations.

Metabolic activity as determined in the MTT assay was used to quantitate crenolanib-mediated cytotoxicity in a number of AML cell lines. Crenolanib was determined to be cytotoxic to the FLT3/ITD-expressing leukemia cell lines Molm14 and MV411, at IC50 values of 7 nM and 8 nM, respectively (Figure 4.3).

[figure not shown]

Figure 4.3. In MTT assays, crenolanib is cytotoxic to MV411 and Molm14 cell lines, with IC₅₀ values of 8nM and 7nM, respectively.²⁷

Cytotoxicity of crenolanib can be attributed to its ability to cause near complete inhibition of phosphorylation of FLT3 and its downstream signaling pathways, demonstrated by p-STAT, p-ERK and p-AKT (Figure 4.4).

[figure not shown]

Figure 4.4. Immunoblot experiments performed in Molm14 cells show that crenolanib inhibits downstream signaling of FLT3 at 10nM.²⁷

Primary leukemic blasts from AML patients bearing mutant FLT3 are killed at clinically achievable concentrations of crenolanib

The cytotoxic effects of crenolanib were evaluated on blasts isolated from AML patients. MTT assays were performed on AML patient samples procured from the John Hopkins University tumor and tissue bank. These included:

a) A newly diagnosed patient with FLT3/D835 mutation

- b) Relapsed, refractory patients with FLT3/ITD AML, who have previously been treated with standard or high dose chemotherapy (N=4)
- c) A refractory AML patient with FLT3/D835 who had previously been treated with FLT3 inhibitors (N=1)

Crenolanib has in vitro activity against blasts with FLT3-D835 mutation, resistant to both sorafenib and quizartinib

Leukemic blasts from a newly diagnosed patient with the FLT3-D835V mutation were resistant to sorafenib and quizartinib but sensitive to crenolanib. Immunoblotting showed that crenolanib inhibited phosphorylation of mutant FLT3, while quizartinib and sorafenib did not, suggesting the greater in vitro efficacy of crenolanib in this subset of FLT3 mutant AML (Figure 4.5).

[figure not shown]

Figure 4.5. Immunoblot experiment performed at 20nM comparing the activity of crenolanib and sorafenib against leukemic blasts with the FLT3-D835V mutation shows that blasts were resistant to sorafenib, while crenolanib provided near complete (>90%) inhibition of phosphorylated FLT3. ²⁷

Crenolanib is cytotoxic to leukemic blasts from relapsed/refractory AML patients with FLT3/ITD mutation

5. CRENOLANIB BESYLATE (CP-868,596-26), CLINICAL DATA

Phase I/II clinical study of oral crenolanib showed that it was well absorbed and well tolerated

Crenolanib has been clinically evaluated as a single agent in a dose-finding and dose-ranging phase-1 study with fifty nine patients treated and was found to have good oral bioavailability. Crenolanib was rapidly absorbed on an empty stomach with a median t_{max} ranging from 1 to 4 hours. The half-life of crenolanib in this Phase I trial was found to be between 13-16 hours.

As of 31 May 2013, no treatment related deaths have been reported in 200 patients treated with crenolanib both as a single agent and in combination. The most frequent non-hematological grade 1/2 toxicities were diarrhea, nausea, and vomiting (Table 5.1). In patients with GIST, anemia was the most frequent grade 1/2 hematological toxicity associated with crenolanib treatment. Four patients required transfusion, though most of these patients had grade 1/2 anemia prior to treatment initiation. The most commonly reported all-causality events of severity Grades 3 or 4 have included LFT increase, anemia, hyponatremia, fatigue and headache.. All LFT abnormalities resolved to baseline or less upon discontinuation of crenolanib. The AML protocol recommends prophylactic antiemetics and anti-diarrheals as well as regular monitoring of hepatic enzymes. Table 5.1 summarizes AEs observed in 126 adult and pediatric patients treated with single agent crenolanib.

Confidential

Protocol: ARO-005

19

		NCI CTC S	Total patients = 126			
Advance Event	GRADE	GRADE	GRADE	GRADE	TOTAL	%
Adverse Event	1	2	3	4	AEs	Patients
Nausea	86	19	2	1	108	63
Vomiting	85	10	4	0	99	55
Diarrhea	62	13	1	0	76	45
Alanine aminotransferase						
increased	32	9	7	2	50	23
GGT increased	33	14	13	3	63	21
Fatigue	16	12	2	0	30	18
Alkaline phosphatase increased	25	10	2	0	37	14
Anorexia	15	5	1	0	21	13
Aspartate aminotransferase						
increased	28	11	6	2	47	13
Lymphocyte count decreased	22	10	7	2	41	13
Headache	14	1	2	0	17	10
Anemia	8	6	4	2	20	10
Abdominal pain	11	2	2	0	15	10
Dyspepsia	7	4	2	0	13	10
Dysgeusia	11	3	0	0	14	9
Constipation	11	2	0	0	13	9
White blood cell decreased	16	4	1	0	21	8
Proteinuria	12	0	0	0	12	7
Edema limbs	11	2	0	0	13	6
Hypophosphatemia	10	0	1	0	11	6
Hypoalbuminemia	8	0	0	0	8	6
Periorbital edema	8	0	0	0	8	6
Serum amylase increased	4	3	0	0	7	6
Dizziness	7	0	0	0	7	5
Platelet count decreased	4	0	0	2	6	5

Table 5.1. Incidence of treatment-related AEs occurring in \geq 5% of the study population treated with single agent crenolanib.

ECG data from patients treated with single agent crenolanib in the phase I trial

Fifty nine patients were treated in the phase I single agent study of crenolanib. ECGs were obtained on all subjects at screening done in triplicate at 2 to 5 minute intervals. Baseline ECG was defined as the closest evaluations prior to the first dose of study drug. The summary of QTc at baseline and on-treatment was provided by overall and dose level for the mean, median, range (minimum, maximum) and the frequencies (n [%] of males with (i) QTc within 431 to 450 msec, (ii) QTc>450 msec; females with (i) QTc within 451 to 470 msec, (ii) QTc>470 msec. Of all subjects examined for ECG at baseline 50.85% had normal values and 49.15% had abnormal value.

Using the Fridericia QTc correction critertia, at baseline, there were no females with >470 msec QTc interval, however 1 male subject reported to have a QTc interval of >450 msec. On study, 4 male subjects had a QTc interval between 431 and 450 msec and 2 female subjects had a QTc interval between 451 and 470 msec. Baseline and worst on study QTc (Fridericia correction) is given in Figure 5.1.

For the Bazett QTc correction, 2 male subjects had a QTc interval >450 msec at baseline and on study 6 male subjects had a QTc interval >450 msec. There were no female subjects with a QTc interval >470 msec at baseline however 1 female subject had a QTc interval >470 msec while on-study. Baseline and worst on study QTc (Bazett correction) is given in Figure 5.1.

Summary of QTc (A. Fridericia correction) Baseline and Worst On-Study Summary of QTc (B. Bazett correction) Baseline and Worst On-Study

A. Treatment Group:	Over All				B. Treatment Group: Ov	ver All			
	Ва	seline	(CP-8	olanib 68,596) On-Study		Ва	seline	CP-8	olanib 68,596 On-Study
	(1)	N=59)				(N	(=59)		
QTc interval			(N	=59)				(N =	=59)
(msec)	n	(%)	n	(%)	QTc interval (msec)	n	(%)	n	(%)
Total (males)	29	(49.2)	29	(49.2)	Total (males)	29	(49.2)	29	(49.2)
Mean QTc	400		408		Mean QTc	418		432	
Median QTc	398		408		Median QTc	413		428	
Min QTc	356		370		Min QTc	365		368	
Max QTc	459		448		Max QTc	489		481	
Total (females)	30	(50.8)	30	(50.8)	Total (females)	30	(50.8)	30	(50.8)
Mean QTc	402		411		Mean QTc	425		436	
Median QTc	400		413		Median QTc	429		437	
Min QTc	357		336		Min QTc	393		374	
Max QTc	449		457		Max QTc	460		497	
431-450 (males)	2	(3.4)	4	(6.8)	431-450 (males)	6	(10.2)	8	(13.6)
451-470 (females)	0	()	2	(3.4)	451-470 (females)	3	(5.1)	9	(15.3)
>450 (males)	1	(1.7)	0		>450 (males)	2	(3.4)	6	(10.2)
>470 (females)	0	(''')	0		>470 (females)	0	(-11)	1	(1.7)

Figure 5.1. Summary of QTc (Fridericia correction (A) and Bazett correction (B)) both baseline and worst on-study

There were only two actual grade 1 QT interval prolongations observed in the 59 patients treated, which resolved without need for study drug interruption. No grade 2/3/4 QT interval prolongation has been observed. The grade 1 QT prolongation was observed in 1/6 patients in the 200mg QD without food cohort and in 1/4 patients in the 60mg BID without food cohort. However no QT prolongation was observed in 280mg QD (N=7) and 340mg QD (N=5) without food cohorts and 60 mg BID (N=8) and 100 mg BID (N=12) with food cohorts.

In the pediatric phase I study of crenolanib being conducted at St. Jude's Children Cancer Center (Memphis, TN) in children with gliomas, no episodes of QT prolongations have been observed to date.

No myelosuppression has been observed, as yet, in patients treated with single agent crenolanib

[figure not shown]
Crenolanib has a K_d for c-kit of 78nM as compared to FLT3 of 0.74nM and could potentially not inhibit c-kit at doses that are adequate to inhibit FLT3. Crenolanib because of its lower affinity for c-kit may have a lower potential to cause delayed marrow recovery in patients with AML. No grade 3/4 myelosuppression has been seen in the adult patients treated to date with crenolanib. In addition, no grey hairs have been observed in any patients treated till-date.

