15.1 Adverse Event Reporting

Protocol: ARO-005

The Investigator or physician designee is responsible for verifying and providing source documentation for all adverse events and assigning the attribution for each event for all subjects enrolled on the trial.

For clarity the information required by the sponsor at baseline is to be captured in the CRFs is:

Forms Title	Content to be captured
'Relevant Medical History' (SC_5_Screening)	Any prior important medical history
'Physical Examination' (SC_6_Screening)	From physical examination during screening
'Baseline Medical history' (SC_7_Screening)	Any current medical history
'Baseline Symptoms' (SC_8_Screening)	Any current symptoms

Table 15.1. Sponsor-Required Baseline Information in CRFs.

Adverse Events (AEs) will be evaluated according to the latest CTCAE version 4.03 and documented in medical record. Principal investigator should review and provide documentation of all baseline comorbidites related to the preexisting conditions and/or current medications prior to initiation of cycle one. These events will not be considered as related to crenolanib treatment. If these events continue during the treatment phase they do not need to be captured in the case report form. Captured AEs include:

- 1) Any new AE regardless of its grade or expectedness post study drug initiation
- 2) Worsening of any expected or unexpected AEs determined by the principal investigator as related to crenolanib

Expected events during leukemia therapy are (all other are considered unexpected and should be captured for reporting as outlined above):

- 1) Febrile or infection episodes
- 2) Coagulation abnormalities
- 3) Epistaxis or bleeding except for catastrophic CNS or pulmonary hemorrhage
- 4) Preexisting side effects related to prior disease specific therapy or ongoing medications for management of non-leukemia conditions
- 5) Myelosuppression and myelosuppression-related events (due to disease)
- 6) Bone, joint, or muscle pain
- 7) Fatigue/malaise
- 8) Weakness
- 9) Shortness of breath
- 10) Nausea and vomiting
- 11) Anorexia
- 12) Electrolyte abnormalities (sodium, potassium, bicarbonate, CO2, magnesium)
- 13) Chemistry abnormalities (LDH, phosphorus, calcium, BUN, protein, albumin, uric acid, alkaline phosphatase, glucose)
- 14) Coagulation abnormalities
- 15) Alopecia

Protocol: ARO-005

General Therapy Related Events:

- 1) Catheter related events (thrombosis, bleeding, infection)

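### Section 5 says single-agent crenolanib has caused no myelosuppression, but its own Table 5.1 lists related cytopenias; this may bias attribution and the capture of worsening baseline cytopenia

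*Combined protocol and SAP*

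**What the plan says.** Section 5 carries the subheading "No myelosuppression has been observed, as yet, in patients treated with single agent crenolanib". It is limited to the single agent, but not by grade or age. The paragraph beneath it adds "No grade 3/4 myelosuppression has been seen in the adult patients treated to date with crenolanib". It also argues, from weak binding to c-kit, that delayed marrow recovery may be less likely in AML.

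Earlier in the same section, "Table 5.1 summarizes AEs observed in 126 adult and pediatric patients treated with single agent crenolanib". The caption describes these events as treatment-related. Four rows are cytopenias. The accompanying text says "In patients with GIST, anemia was the most frequent grade 1/2 hematological toxicity associated with crenolanib treatment", and mentions four patients who were transfused, most of whom already had grade 1 or 2 anemia before treatment.

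Section 15.1 decides what becomes an adverse event record:

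- A new event is captured whatever its grade and whether or not it was expected.
- Worsening is captured when the principal investigator judges it related to crenolanib.
- Conditions documented at baseline are treated as unrelated and, if they continue, need not be entered on the case report form (CRF).
- Myelosuppression is on the list of expected events, with the qualifier that it is due to the disease.
- Hematology results from scheduled visits, and transfusion information throughout, go on the CRF.

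**The concern.** Safety and tolerability form a primary objective (Section 1.1). Section 10.3 recognises that patients with leukemia usually start with abnormal counts. The usual question about a cytopenia on study is therefore whether an existing one has worsened. For worsening, Section 15.1 makes the investigator's view of cause the condition for capture. A protocol that says the drug has not caused myelosuppression pushes that view in one direction.

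Little else in the plan would reveal a resulting error. The stopping rule in Section 16.1 counts only non-hematologic toxicity attributed to the drug. Section 16.4 provides general descriptive safety statistics but specifies no analysis of blood counts or transfusions. There is no comparator arm. What is at stake is an adverse event table with too few cytopenias, and too few of them attributed to crenolanib.

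**Working it through.** **Inputs.** All counts come from Table 5.1. Its caption begins "Incidence of treatment-related AEs occurring in" and refers to the "study population treated with single agent crenolanib", with a 5% threshold for inclusion. The lymphocyte row reads "Lymphocyte count decreased 22 10 7 2 41 13": grades 1 to 4, total events, percent of patients.

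| Row | G1 | G2 | G3 | G4 | Printed total | % of 126 |
|---|---|---|---|---|---|---|
| Lymphocytes decreased | 22 | 10 | 7 | 2 | 41 | 13 |
| Anemia | 8 | 6 | 4 | 2 | 20 | 10 |
| White cells decreased | 16 | 4 | 1 | 0 | 21 | 8 |
| Platelets decreased | 4 | 0 | 0 | 2 | 6 | 5 |

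**Step 1: is the table read correctly?** 22+10+7+2 = 41; 8+6+4+2 = 20; 16+4+1+0 = 21; 4+0+0+2 = 6. All four rows match their printed totals, so a misread cell is unlikely.

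**Step 2: compare with the stated figure, which is zero.**

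| Definition | Any grade | Grade 3-4 | Grade 4 |
|---|---|---|---|
| All four rows | 41+20+21+6 = 88 | 9+6+1+2 = 18 | 2+2+0+2 = 6 |
| Without lymphopenia | 88-41 = 47 | 18-9 = 9 | 6-2 = 4 |
| White cells and platelets only | 21+6 = 27 | 1+2 = 3 | 0+2 = 2 |

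The zero is not reproduced under any of these definitions.

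**Step 3: events or patients?** The grade columns count events. Working back from rounded percentages of 126 gives patients with any grade: lymphocytes 16-17, anemia 12-13, white cells 10, platelets 6. One patient may appear in several rows. The number with at least one listed cytopenia therefore lies between 16 (complete overlap) and 17+13+10+6 = 46 (no overlap). The number of patients with any grade 3-4 cytopenia cannot be derived.

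**Step 4: the adults-only sentence.** The table does not split adults from children. For the sentence to be true, all 18 grade 3-4 events would have to be pediatric, or those in adults would have to be classed as something other than myelosuppression. The documents neither show nor exclude this.

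**Step 5: follow a cytopenia through Section 15.1.**

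| Situation | Adverse event record? | Other record |
|---|---|---|
| New cytopenia | Yes, without a test of cause | Scheduled counts, transfusions |
| Baseline cytopenia that continues | Need not be entered | Scheduled counts, transfusions |
| Baseline cytopenia that worsens | Only if judged related to crenolanib | Scheduled counts, transfusions |

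Only in the third line does the investigator's view of cause decide whether an event is captured. If a site treats a rise in grade as a new event, the first line applies instead, but the separate rule for worsening points the other way. The documents do not give the proportion of patients who start cytopenic, so the amount of under-capture cannot be estimated.

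**The case against.** The strongest reply is that the contradiction sits in a background section and the rest of the protocol limits the damage. Much of that stands.

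- New events are captured without regard to expectedness, and counts and transfusions are on the CRF. This stands: the raw data are not lost.
- The protocol does contemplate cytopenia caused by the drug. Sections 9.2 and 10.3 allow interruption or adjustment for prolonged low counts. Sections 12.3 and 13.2 and Appendix V provide, at loss of CR, for a marrow examination as clinically indicated to tell pancytopenia from study drug apart from progression. This stands.
- The expected-event item is limited to disease-caused myelosuppression, so drug-caused myelosuppression falls outside it. This stands in part: sorting an event into one or the other is the same judgment of cause.
- Investigators also see Table 5.1 and the remark on anemia, so the message is mixed rather than a plain denial. This stands.
- The size can be overstated. Lymphopenia supplies 41 of the 88 events and 9 of the 18 at grade 3-4, falls in lymphocytes and white cells may overlap, and the table has no neutrophil row. This stands, but white cells and platelets alone still give 27 events, 3 of them grade 3-4.

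A reader might infer that drug-caused cytopenia will be put down to leukemia and go unreported. The first two replies show that the documents do not support this. A reader might also infer that the adults-only grade 3/4 sentence is false. A pooled table cannot show that.

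**Conclusion.** The subheading in Section 5 is incompatible with Table 5.1: zero stated, against 88 related events with 18 at grade 3-4, or 27 and 3 on the narrowest of the definitions tried. This rests on the caption's description of the events as treatment-related and on counting falls in blood cells as myelosuppression.

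The consequence is a risk, not a certainty. The statement may bias attribution, and worsening of a baseline cytopenia may be under-captured as an adverse event, because that is where Section 15.1 makes capture depend on relatedness. The size of this effect cannot be calculated from the documents. It touches a primary objective and is cheap to correct, so the change should be made.

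**What to change.** 1. **Section 5.** Reconcile the subheading and the adults-only sentence with Table 5.1. Give adult and pediatric counts for each cytopenia by grade, in patients as well as events, and say which cytopenias are classed as myelosuppression.

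2. **Section 16.4.** Add a safety summary that ignores attribution, by cohort: shift tables from baseline to worst CTCAE grade for hemoglobin, neutrophils and platelets, and a summary of transfusion use. The protocol refers only to transfusion information, so whether units can be reported depends on the CRF field.

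State the limits with the tables:

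- In a single-arm trial they cannot by themselves separate drug from disease.
- Patients already at grade 4 for neutrophils or platelets cannot shift upward.
- Results outside scheduled visits are recorded only if they led to a dose change or delay, and counts are monthly from cycle 3, so some low points will be missed.
- Any split by residual marrow leukemia at cycle 2 day 1 is optional and should be labelled descriptive, because it conditions on a post-treatment outcome.

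The cost is one corrected paragraph and a few tables from data already on the CRF. The change requires no dose or clinical management rule, and none is proposed.
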